	SD	681	2.80	4,021	6.30	26.68	
	Median	899	5.00	8,497	2.61	29.42	

|--|

The PK studies in human confirm the short elimination half-life of the product, and that the systemic clearance (CLs) values demonstrate that the clearance processes involved are of high capacity and rate.

Efficacy results: Analysis of results from the Phase 2a study, indicated that patients in the AB103 treatment groups had a substantial improvement in their clinical status across

multiple endpoints when compared to patients in the placebo group. Patients in the AB103 0.50 mg/kg and AB103 0.25 mg/kg treatment groups had a continuous resolution of organ dysfunction over time without subsequent worsening. Although not statistically significant, AB103 treated patients had a trend of spending fewer days in ICUs, requiring fewer days of assisted ventilation, and needing fewer surgical procedures to remove necrotic tissue. In addition, treatment of patients with AB103 reduced the levels of both systemic and local tissue cytokines and chemokines in a dose dependent manner. Tissue biomarkers, especially in the margins of the lesion, had reduced levels of cytokines, suggesting that administration of high dose AB103 may reduce progression of inflammation in marginally involved tissues. The overall tissue and systemic biomarkers are consistent with the mechanism of action of AB103, as attenuating the inflammatory response and possibly reducing the zone of tissue injury. The summary of the results is presented in Table 3 below:

	Placebo	0.25 mg/kg	0.5 mg/kg
Days in ICU	8.9	4.9	5.4
Days on Ventilator	5.2	3.1	2.7
SOFA score Day 14*	2.7	1.1	0.7
% patients with organ failure at Day 14	40	14.3	7.1
(defined as SOFA score ≥ 3)			
% patients with organ dysfunction at Day 14 *	66.7	37.5	11.1
(defined as SOFA score ≥ 2)			
% of patients with only 1 debridement	20	26	33
% of patients with \geq 4 debridement	30	20	13
% Mortality	20	6.7	6.7

Table 3: Consistent response across multiple clinically relevant end points

*P<0.05

Based on the reproducibility of the dose response in the various parameters, the 0.5 mg/kg dose was chosen for further clinical development.

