4.3.4 Visit 4 (Day 3)

- Collect data on operative procedures
- Obtain tissue for microbiology if debridement performed on Day 3
- Collect data on acute renal replacement therapy
- Collect data on plasma or platelet transfusion
- Urine output (should be recorded continuously from time of ICU admission to Day 7, if still in ICU and Foley catheter in place, using 6 hour intervals and by calendar

day). Collection of AEs/ SAEs including secondary infections (based on CDC definitions for healthcare associated infections)

- Collect data on additional amputations
- Concomitant medications
- Vital signs (to be taken during the morning tests)
- Symptom-driven interim PE
- Evaluation of adequacy of antimicrobial treatment, based on results from susceptibility testing once the data is available
- Critical care parameters (dates and times of assisted ventilation, vasopressor use, ICU /hospital stay)
- Systemic response: mSOFA score (measurements will be collected and scores will be calculated retrospectively)
 - All efforts should be made to obtain the actual measurements of SOFA parameters at these visits-may use SpO2 value (and record FiO2) if arterial blood gas is not clinically indicated
 - Obtain serum creatinine
 - Obtain CBC with differential and platelet count (sample can be same as that required to be taken in conjunction with the RNA expression profile test sample)
- Assess lesion status (healing/progression/significant change in appearance) if accessible for visible assessment at time of debridement or routine dressing change
- Collect whole blood for leukocyte transcriptome (RNA expression) profiling
 - CBC with differential required to be obtained in conjunction with sample for RNA expression profile best
- Record Survival

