6.2.15 Microbiology

Microbiological testing will follow the SoC of treatment of NSTI patients. At the time of initial surgical exploration, and if surgical debridement is performed on study Day 3, a tissue sample will be cultured by the local microbiology laboratory.

The deep tissue specimens will be obtained at the time of the first debridement at the operating room at the study site medical center. Antibiotics received prior to the primary surgical debridement will be identified as well as antibiotics received during the study evaluation window of Days 1-28.

A specimen of infected tissue will be taken from the infected area, will be placed in a sterile container and transported by hand to the local designated clinical microbiology laboratory at the institution and according to the approved methods of each medical center. The specimens will then be processed as soon as possible by homogenization, the homogenate will be Gram stained, and cultured under 2 different conditions for testing of aerobic and anaerobic pathogens

Cultures of the NSTI wound will be obtained according to the schedule of events on Section 15.1. Bacterial isolates obtained from the patients in the study, and considered to be pathogens will be identified by genus and species using the methods established in the *Manual of Clinical Microbiology*⁴⁰. Results will be used to categorize patients according to microbiology organism group (Gram-positive, Gram-negative, anaerobic, mixed infection).

Susceptibility testing will be performed on all aerobic pathogens according to clinical laboratory standards institute (CLSI) criteria.

Blood culture for both aerobic and anaerobic bacteria will be taken during screening process. Repeat blood cultures for microbiology will also be obtained according to physician discretion, if the patient is suspected to have a new or progressive infection (if deterioration in the hospitalized patient's condition is observed (e.g. spiking a fever).

Bacterial isolates identified as *Streptococcus pyogenes* or *Staphylococcus aureus* will be stored frozen at the site and shipped to the Central Microbiology Laboratory (IHMA, Schaumburg, IL) for future testing. Instructions for freezing, storage and shipping of the bacterial isolates can be found in a separate Laboratory Manual for the study.

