7.2 Secondary Measures

- 5 component clinical composite endpoint but with mSOFA ≤ 1 at Days 21 and 28
- Distribution of mSOFA scores at Days 14 and 21
- Kaplan-Meier analysis of the time to resolution of mSOFA score to ≤1 with censoring at Day 14
- Single components of the composite end point
 - Alive at Day 28
 - Number of patients with debridements by Day $14 \le 3$
 - Number of amputations (excision to a joint space) (done after first debridement)
 - mSOFA score on Day $14 \le 1$
 - Reduction of \geq 3 score points between Baseline and Day 14 mSOFA score.
 - Critical care and hospital stay parameters, to be measured until Day 28
 - o ICU-free days
 - Days in ICU
 - Days on ventilator
 - Ventilator free days
 - Vasopressors days/ Vasopressors free days
 - Hospital length of stay (days)
- Clinical local parameters:
 - Number of debridement to days 7, 10, 14 and 28
 - Proportion of patients needing (up to Day 14):
 - 1. only one debridement to control the infection
 - 2. \geq 2 debridements to control the infection
 - 3. \geq 3 debridements to control the infection

- Clinical systemic parameters:
 - Evaluation of organ function over time, using mSOFA score
 - Recovery from AKI

7.3 Exploratory Measures:

- Evaluation of blood leukocyte transcriptome (RNA expression) profiling in patients with NSTI and compare genomic profile in patients treated with AB103 versus placebo
- Evaluation of the clinical response by baseline pathogen
- Evaluation of the microbiological outcome in the microbiological evaluable population
 - *By-Pathogen Bacteriological Response:* The by-pathogen bacteriological response for each causative organism identified at baseline (BL) will be defined as follows:
 - Eradication: BL causative organism cannot be isolated from any culture(s) obtained from a debridement performed on or after study Day 3.
 - Persistence: The BL causative pathogen is isolated from a debridement performed on or after study Day 3.
 - *By-Patient Bacteriological Response:* The by-patient bacteriological response will be determined according to the following definitions:
 - Eradication: All BL causative organism(s) have a response of Eradication.
 - Persistence: All or some BL causative organism(s) have a response of Persistence.
- Evaluation of plasma and urinary biomarkers in patients with AKI
- Data (including financially related data) will be gathered to evaluate possible health economic outcomes from the study, including but not limited to:

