^q Tissue for microbiology will be taken at the 1st debridement (performed at visit 1), to be used for identification of pathogen(s), susceptibility to antimicrobial drugs and Gram stain. Obtain tissue for microbiological culture if debridement performed on Day 3 (Visit 4). If culture from debridement on Day 3 is positive, then repeat culture if subsequent debridement(s) performed.

^r Adverse events including SAEs will be collected from obtaining ICF through day 28; AEs that are not resolved should be followed-up until resolution or until determined as stable and due to known cause.

^s AEs of day 0 are baseline AEs (not TEAE) starting after obtaining ICF until study drug administration.

^t Assess lesion status (healing/progression/significant change in appearance) if accessible for visible assessment at time of debridement or routine dressing change

Visit	1	2	3	4	5	6	7	8	9	10
	Screening	Day 1	Day 2	Day 3	Day 7 ±1 day	Day 10 ±1 day	Day 14 ±1 days	Day 21 ±1 days	Day 29 +2 days	3 months ±5 days
Collect data on acute renal replacement therapy, plasma and/or platelet transfusion									•	
Evaluation of adequacy of antimicrobial treatment				Х						
Critical care and hospital stay parameters ^u										
mSOFA score ^v	Х	X ^w	Х	Х	Х	Х	Х	Х	Х	
APACHE II score ^x	X									
LRINEC and Anaya ^y scores	Х									
Survival										
Hospital readmissions ^z									Х	Х
Serum for immunogenicity ^{aa}	X						Х		Х	X

^u Hospital length of stay (days), ICU stay (days), ICU free days, Mechanical ventilation days/mechanical ventilation free days;

^v Screening mSOFA: To be calculated prospectively from time patient presents at the hospital (may include referring hospital) but within 6 hours prior to first debridement. Screening mSOFA may be reassessed up to actual time of surgery if initial mSOFA evaluation had score <3. To include measurements of 5 organ systems to achieve score of \geq 3, in any one or more organs, with any one organ having a score of at least 2: cardiovascular, respiratory, renal, coagulation and CNS (To include evaluation of oxygenation either directly by arterial blood gas test or by calculation of PaO₂ from SpO₂, in case it is not possible to obtain arterial blood to determine the SOFA respiratory parameter), ^w Subsequent mSOFA data collection (Days 1, 2, 3, 7, 10, 14, 21 and 29): taken once a day, in the morning (between 6AM until 12 noon) adjusted to the time of normal

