4.7 Microbiology

By-Pathogen and By-Patient bacteriological responses will be summarized as follows:

- o *By-Pathogen Bacteriological Response:* The by-pathogen bacteriological response for each causative organism identified at baseline (BL) will be defined as follows:
 - Eradication: BL causative organism cannot be isolated from any culture(s) obtained from a debridement performed on or after study Day 3.
 - Persistence: The BL causative pathogen is isolated from a debridement performed on or after study Day 3.
- o *By-Patient Bacteriological Response:* The by-patient bacteriological response will be determined according to the following definitions:
 - Eradication: All BL causative organism(s) have a response of Eradication.
 - Persistence: All or some BL causative organism(s) have a response of Persistence.

Presence of pathogens will be determined using blood and tissue cultures. Treatment group comparisons of response rates will only be performed if there at least 5 instances of a unique pathogen in both groups and are limited to patients with microbiological samples at screening and at follow-up (i.e., day 3). By-patient microbial responses will be based on worst response.

Pathogens will also be categorized into Gram-positive / Gram-negative and into aerobic and anaerobic sub types.

Prevalent sub types and classes of identified pathogens will be used in sub group analyses of clinical response as described above.

5 Analysis Approaches

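### SAP 4.7 compares bacteriological response only in patients with a Day 3 follow-up sample, so the comparison conditions on a post-dose event that treatment is expected to change

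*SAP*

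**What the plan says.** SAP 4.7 and Protocol 7.3 define eradication in the same way: "BL causative organism cannot be isolated from any culture(s) obtained from a debridement performed on or after study Day 3". Persistence is isolation of the baseline pathogen from such a debridement. SAP 4.7 adds that "Presence of pathogens will be determined using blood and tissue cultures", that response rates are compared only "if there at least 5 instances of a unique pathogen in both groups", and that the comparisons "are limited to patients with microbiological samples at screening and at follow-up (i.e., day 3".

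The protocol says when follow-up tissue exists:
- Section 4.3.4 (Visit 4): "Obtain tissue for microbiology if debridement performed on Day 3".
- Section 6.2.15: "At the time of initial surgical exploration, and if surgical debridement is performed on study Day 3, a tissue sample will be cultured".
- Appendix A, tissue footnote: "Obtain tissue for microbiological culture if debridement performed on Day 3 (Visit 4". A later culture is called for only when the Day 3 culture was positive and the patient is debrided again.

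No blood culture is scheduled at Day 3. Under Section 6.2.15, repeats are at the physician's discretion when new or progressive infection is suspected. Study drug is given during or after the first surgery (Section 4.2.2), so Day 3 is after dosing. Section 2.4 names fewer debridements to Day 14 as an expected effect of the drug.

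Protocol 2.3 and 7.3 refer to a microbiologically evaluable population, but neither Protocol 9.2.2 nor SAP 2.6 defines one. The SAP gives no rule for patients without a follow-up culture and no sensitivity analysis for their absence.

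**The concern.** Whether a patient enters the comparison is decided after dosing, by an event on the pathway the drug is meant to alter. Even with balanced arms at randomisation, the sampled patients in the two arms need not be alike, and a difference in their eradication rates can arise with no effect on bacterial clearance. SAP 5.9 itself gives selective exclusion from treatment groups as the reason for intent-to-treat comparisons. For free-day outcomes, SAP 4.3 takes care over the similar problem of death removing patients from risk. SAP 4.7 has no such safeguard.

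At stake is the reading of one exploratory result. It bears on a question readers will ask of an immunomodulator: does it impair clearance of the infecting organism? A selected comparison could falsely reassure or falsely alarm.

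There is also a mismatch of wording. A patient first re-debrided on Day 4 fits the response definition, yet the protocol requires no culture and the SAP restriction points to Day 3.

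**Working it through.** **The plan's own figure.** The documents give no figure for this comparison. The primary sizing figure (80.2% power; 145 per arm; difference 0.20 centred on 0.5; two-sided 0.01) reproduces: (0.20 - 2.576 x sqrt(0.5/145)) / sqrt(0.48/145) = 0.847, and the normal probability below that is 80.2%. Nothing below depends on it except the 145 per arm.

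**Ceiling on who can be sampled.** Protocol Table 3 gives the percentage "of patients with only 1 debridement" in Phase 2 as 20% on placebo and 33% at 0.5 mg/kg. A patient with one debridement has no follow-up tissue. If those shares applied here:
- placebo: 145 x (1 - 0.20) = 116
- active: 145 x (1 - 0.33) = 97

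The documents do not give the share debrided on Day 3 itself. If it were 25%, 50% or 75% of patients with two or more debridements, the sampled numbers would be about 29 vs 24, 58 vs 49, or 87 vs 73.

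**No drug effect on clearance, one extreme of selection.** Assume the same true eradication rate E in both arms, an unsampled share u of 0.20 (placebo) or 0.33 (active), and every unsampled patient truly eradicated. The rate seen among sampled patients is (E - u)/(1 - u).

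| True rate, both arms | Placebo, sampled | Active, sampled | False difference (points) |
|---|---|---|---|
| 50% | 37.5% | 25.4% | -12.1 |
| 60% | 50.0% | 40.3% | -9.7 |
| 70% | 62.5% | 55.2% | -7.3 |
| 80% | 75.0% | 70.1% | -4.9 |

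**Other selection patterns.** Let h be the chance that a truly persistent patient goes unsampled, relative to a truly eradicated one. The unsampled share among eradicated patients is then v = u/(E + h(1 - E)), and the sampled rate is E(1 - v)/(1 - u). At E = 60%:

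| h | Placebo, sampled | Active, sampled | False difference (points) |
|---|---|---|---|
| 0 | 50.0% | 40.3% | -9.7 |
| 0.25 | 53.6% | 47.3% | -6.2 |
| 0.5 | 56.2% | 52.6% | -3.6 |
| 1 | 60.0% | 60.0% | 0 |
| 2 | 64.3% | 68.4% | +4.2 |

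The last row represents unsampled patients who are disproportionately early deaths or uncontrolled infections; the sign reverses. The documents give no basis for choosing a value of h.

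**Documented persistence over all patients is not a cure.** Take h = 1, where the sampled comparison is unbiased, with true persistence 40% in both arms. Documented persistence is 0.40 x 0.80 = 32.0% on placebo and 0.40 x 0.67 = 26.8% on active. That is a false 5.2-point advantage for the drug, produced only by taking fewer cultures.

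**The case against.** The strongest reply is that little hangs on this. The measure is exploratory, and SAP 5.6 makes no attempt to control type 1 error beyond the key secondary endpoint. SAP 4.7 names no test. The table list in SAP Appendix 1 has baseline pathogens (14.1.3.5) but no bacteriological response table. Infection safety is covered elsewhere: secondary infections are collected at visits, and infection adverse events are tabulated in all treated patients (SAP 9.1.6, Table 14.3.1.14). All of this stands and limits the weight of the point. It does not make the planned comparison valid.

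SAP 4.7 also admits blood cultures, and the protocol does not bar routine cultures on other days, so Day 3 surgery is not strictly the only way in. That stands too, but discretionary cultures prompted by suspected infection are another post-dose selection.

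Two stronger readings are tempting and the documents do not support them. A reader might infer that most patients cannot be evaluated; the share debrided on Day 3 is not given. A reader might also infer that the best responders are the ones left out, so the bias runs against the drug. The unsampled group also holds patients re-debrided on other days and early deaths, so the direction is unknown.

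The Phase 2 shares are weak evidence. The table gives percentages only, from a 40-patient study. If the groups were about 10 and 15 (inferred), the contrast is 2/10 vs 5/15, Fisher p about 0.66, and the protocol itself describes the trend to fewer procedures as not significant.

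**Conclusion.** The point holds as a local flaw in an exploratory analysis. The comparison in SAP 4.7 is conditioned on a post-dose event that treatment is expected to change, so it lacks the protection of randomisation. The response definition also does not match the sampling and restriction wording.

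The size cannot be fixed from the documents. With Phase 2 one-debridement shares and a true rate of 60% in both arms, the false difference runs from -9.7 to +4.2 points over the selection patterns tried. It is zero if sampling is unrelated to clearance. These figures rest on assumed rates and selection patterns, and on Phase 2 shares from few patients. NICCE, the conditional co-primary endpoint, the key secondary AKI endpoint and the sample size are untouched.

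**What to change.** In SAP 4.7, before unblinding:

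1. Define the evaluable set as all mITT patients with a baseline pathogen, and use it as the denominator.
2. Tabulate four categories by arm, with the number sampled per arm: documented persistence; documented eradication; presumed eradication (alive, with no debridement on Day 3 or later); and indeterminate (early death, or debrided without culture). State the day to which alive is assessed.
3. Show the arm difference under bracketing assumptions, for example presumed and indeterminate both as eradicated, then indeterminate as persistent. Moving from the first to the second lowers each arm's eradication rate by its own indeterminate share. Do not rely on documented persistence alone.
4. Keep the sampled-only comparison as descriptive, without a p-value.
5. Reconcile the Day 3 wording with the Day 3 or later wording across Protocol 6.2.15, the Appendix A tissue footnote and SAP 4.7.

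Steps 1 to 4 cost a SAP edit and one added table; no listed response table has to be discarded. If step 5 is settled by changing when tissue is cultured, it changes specimen collection at about 75 sites, needs a protocol amendment, and cannot recover cultures never taken. If it is settled in the SAP, it is wording only.

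The downside is that presumed eradication is an inference, and counting it as eradication credits an arm for fewer operations. It is therefore shown separately. The brackets show how far the result depends on unsampled patients; neither is an unbiased estimate.

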5.1 Baseline Comparisons

Demographic and baseline characteristics will be summarized for each analysis set overall and by treatment group. Categorical variables including race, ethnicity, and gender will be summarized by counts and percentages. Continuous variables will be summarized using mean, median, standard deviation (SD), and minimum and maximum values. Continuous variables evaluated will include age, BMI, height, weight, systolic BP, diastolic BP, MAP, heart rate, and temperature; as well as ANAYA, LRINEC, and APACHE II scores. Presence of baseline sepsis will be summarized according to the numbers and percentages of patients with baseline cardiovascular and respiratory organ failure as reflected in screening component SOFA scores of 3 or 4. In addition presence of any AKI at baseline algorithmically determined, Stage 2/3 AKI at screening, and maximal AKI Stage 2/3 as assigned by the blinded adjudication panel will be summarized.

Analyses will be performed to confirm that the randomization resulted in no clinically significant group differences at baseline. Although emphasis will be on clinical significance, baseline comparisons will include t-tests or Wilcoxon rank-sum tests as appropriate for interval variables and chi-square or Fisher's exact tests as appropriate for nominal variables to aid in the screening for baseline differences. If there are clinically important baseline differences, multiple logistic regression will be used in supporting analyses to assess the impact of the imbalance on significance levels.

5.2 mSOFA

The Sequential Organ Failure Assessment score or SOFA was originally developed to track a patient's status during a stay in an intensive care unit (ICU)⁸,⁹. Each of six organ systems are evaluated (see Appendix 5) with ordinal scores 0 to 4. A total score is the sum of the component scores. For this study, the liver component is excluded and the resulting sum score is referred to in this study as 'mSOFA'.

Several approaches will be taken to summarize changes over time and between treatment groups in the clinical scores as described below.

mSOFA scores will be assessed as 1) observed cases, 2) last observation carried forward (LOCF), 3) using MMRM, and 4) categorized and combined with mortality and local activity as part of the primary composite clinical success endpoint, NICCE.

The following will be defined as OBSERVED mSOFA.

1. If a single individual organ score is missing but other scores for that day are non-missing, the organ system that were not evaluated are assumed to be free of organ failure and are given a value of zero when determining the sum score.

⁸ Vincent JL, Moreno R, Takala J, et al: The SOFA (Sepsis-related Organ Failure Assessment) score to describe organ dysfunction failure: On behalf of the Working Group on Sepsis-Related Problems of the European Society of Intensive Care Medicine. Intensive Care Med 1996; 22:707–710.

⁹ Vincent JL, Angus DC, Artigas A, Kalis A, Basson BR, Jamal HH, Johnson III G., Bernard GR for the PROWESS Study Group. Effects of drotrecogin alfa (activated) on organ dysfunction in the PROWESS trial. Crit Care Med 2003; 31:834 – 840.

2. If two or more individual organ scores are missing for mSOFA on Day 14 or earlier, but at least one individual organ score is non-missing, the individual organ scores will be imputed using last observation carried forward. In this case, it is possible that different components come from different visits. This will not be done at Day 21 and Day 28.

The following will defined mSOFA LOCF.

- 3. If all organ scores are missing on Day 14 or earlier, the mSOFA total score from that day will be imputed using last observation carried forward with the following exception.
 - a. LOCF will not be performed after patient death.
 - b. Note that LOCF will not be performed for unavailable mSOFA total scores at Day 21 and Day 28.
- 4. When summarizing the individual organ scores apart from the mSOFA total scores, the same rules as above will apply.
- 5. Patients with recorded screening mSOFA inflated by GCS scores due to mechanical ventilation or due medications will have their GCS score removed when determining screening mSOFA. This is to prevent subjects meeting trial inclusion just on the basis of GCS.

Since LOCF will not be applied to missing mSOFA scores after patient death in analyses that employ LOCF to describe mean values of time, there may be some 'diminishing n' and focus is therefore on morbidity rather than mortality.

